# 6.5. Continued Access to Study Intervention after the End of the Study

The investigator is responsible for ensuring that consideration has been given to the post-study care of the participant's medical condition.

Refer to the Schedule of Assessments for follow-up assessments of participants who are to be followed for disease progression and/or survival after they permanently discontinue from study intervention.

# 6.6. Treatment of Overdose

For this study, any dose of GSK3745417 greater than 50% within a 24-hour period will be considered an overdose.

GSK does not recommend specific treatment for an overdose.

In the event of an overdose, the investigator/treating physician should:

- 1. Contact the Medical Monitor immediately.
- 2. Closely monitor the participant for AE/SAE, vital signs, and laboratory abnormalities for at least 24 hours, and longer if clinically indicated or recommended by the medical monitor based on safety data obtained from the study
- 3. Obtain a blood sample for PK analysis as soon as possible following the study intervention if requested by the Medical Monitor (determined on a case-by-case basis)
- 4. Document the quantity of the excess dose as well as the duration of the overdosing in the CRF.

Decisions regarding dose interruptions or modifications will be made by the investigator in consultation with the Medical Monitor based on the clinical evaluation of the participant.

# 6.7. Concomitant Therapy

# 6.7.1. Permitted Medications

Participants considered to have an increased risk of thrombosis (e.g., history of catheter related clots, DVT) can be considered for prophylactic anticoagulation per local practice and/or clinical judgement.

Prophylaxis for CRS is not mandated. However, if a participant has CRS, prophylaxis with antihistamines and paracetamol /acetaminophen is permitted on subsequent infusions. NSAIDs for fever or symptoms control should be avoided due to risk of renal injury.

Participants receiving hormonal therapy for a definitively treated malignancy (e.g., adjuvant therapy of localized breast or prostate cancer) may continue to receive therapy during study, after discussion with the medical monitor.

Erythropoiesis-stimulating agents and colony-stimulating factors like filgrastim and pegfilgrastim may be used as clinically indicated for treatment of cytopenias. If used, these agents should be held for a period prior to disease assessment, per local institutional practice or guidelines.

## 6.5.2. Prohibited Medications and Non-Drug Therapies

The following medications are prohibited before the first dose of study treatment (see Section 5.2 for specific time requirements) and while on treatment in this study:

- Any investigational drug(s)
- Other anticancer therapy (chemotherapy, radiation therapy [unless administered palliatively], immunotherapy, biologic therapy, or hormone therapy other than for replacement).
  - Note: participants receiving hormonal therapy for a definitively treated malignancy (e.g., adjuvant therapy of localized breast or prostate cancer) may continue to receive therapy during study, after discussion with the medical monitor.
- Live vaccines or live attenuated vaccines including herpes zoster, nasal flu, and coronavirus vaccines, as well as recombinant human or non-human primate adenoviral vector vaccines.

Concomitant administration of drugs that are sensitive substrates or narrow therapeutic range substrates for cytochrome p450 (CYP) 3A4 enzyme, P-gp, BCRP, OATP1B1 and OATP1B3 transporter, and moderate to strong inducers and inhibitors of CYP3A4, P-gp, OATP1B1 and OATP1B3 should be excluded during the study and for 7 days prior to and following treatment with GSK3745417 (14 days for itraconazole),. Note: any medications (including antibacterials, antifungals, and antivirals) which are necessary for the health, wellbeing, or standard clinical care of patients with hematologic malignancies are exempt from this restriction. Any medications potentially interacting with GSK3745417 will require a pause in GSK3745417 dosing unless allowed through consultation with the Sponsor. Refer to the Study Reference Manual for a detailed list of excluded drugs.

# 7. DISCONTINUATION OF STUDY INTERVENTION AND PARTICIPANT DISCONTINUATION/WITHDRAWAL

In some instances, it may be necessary for a participant to permanently discontinue study intervention. If study intervention is permanently discontinued, the participant will remain in the study to be evaluated for disease status / progression and survival. See the SOA for data to be collected at the time of discontinuation of study intervention and follow-up and for any further evaluations that need to be completed.

# 7.1. Discontinuation of Study Intervention

## 7.1.1. Liver Chemistry Stopping Criteria

Liver chemistry stopping and increased monitoring criteria have been designed to assure participant safety and evaluate liver event etiology.

Discontinuation of study intervention for abnormal liver tests is required when a participant meets one of the conditions outlined in Figure 6.

Refer to Section 10.7 for required Liver Safety Actions and Follow up Assessments and for required process for study intervention restart/rechallenge if considered for the participant.

## 7.1.2. Renal Stopping and Increased Monitoring Guidelines

Renal events are to be managed as outlined in Table 13.

#### Table 13 Guidelines for Dose Modification and Management of Renal Events

Adverse Event	Management
Serum Creatinine Increase by >0.3 mg/dL or 26.5 µmol/L Compared to Baseline	
 
Hold Study Treatment unless considered related to TLS (see Section 6.4.1.2)
 
Repeat serum creatinine levels at least every 24 hours, monitor urine output
 
Perform diagnostics to identify root cause
 
Nephrology consultation is highly recommended
 
Discuss with Sponsor/Medical Monitor if considering resuming study drug treatment after initial hold
 
If serum creatinine is Grade 2 or higher for more than 7 days without a known cause, permanently discontinue treatment (unless continued dosing is approved by Medical Monitor)
 
If renal injury is considered secondary to TLS (for example, an increase in creatinine in association with increasing blood phosphate and uric acid levels), treatment may be continued (without hold) with the agreement of the Medical Monitor. In such cases, consider close monitoring of urine output and urinary pH, and early nephrology consultation
 

Abnormal urinalysis findings, including hematuria	
 
Perform diagnostics to identify root cause
 
Consider holding study treatment (though patients with abnormal findings consistent with TLS such as urate crystals may continue dosing as agreed by investigator and Medical Monitor)
 
Nephrology consultation is highly recommended if cause is not known
 

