In Part 1, participants will receive dosing in the hospital on a 5 days on/2 days off schedule for 2 weeks, and then have an additional 2 weeks off dose for observation. The participant will be observed for at least 24 hours after the final dose in each cycle. All participants will be hospitalized the day before a new dosing cycle starts to receive tumor lysis syndrome (TLS) prophylaxis in line with institutional guidelines (all participants should receive IV fluids  $\pm$  allopurinol as well as alkalinization of urine with renal consult if this is in line with institutional guidance). TLS prophylaxis will continue alongside daily dosing as clinically indicated. To further reduce the risk of TLS, guidance in Section 6.4.1.2 must be followed to determine when daily dosing should be held.

Additional cohorts TBD based on emerging data

209809

\* Patients in C3 dose level in all cohorts will be continuing dosing Q1W at C3 dose level

### Part 2

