## Holding daily dosing

Daily dosing will be continued unless there is evidence of ongoing TLS or immune activation in line with the criteria below.

Daily dosing held if:

- Ongoing Grade 3 TLS (see Appendix 11 for Cairo Bishop grading) or Grade 3 electrolyte abnormalities that are not responding to treatment
- Failure of any CRS, fevers, or chills to resolve to Grade ≤1 (with supportive treatment) within 24 hours
- Any new neurological adverse events (except for Grade ≤2 headache which responds to analgesia), until assessment and cause of neurological event is identified
- Investigator judgement that dosing should be held based on the clinical status of patient

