## 6.4.1.2. Tumor Lysis Syndrome

Tumor lysis syndrome (TLS) may occur in participants treated with GSK3745417 as it has demonstrated a direct cell killing mechanism in AML cells. Laboratory or Clinical TLS should be diagnosed according to the Cairo Bishop criteria (Cairo, 2004). In the event of TLS, Investigators should use clinical judgement and follow institutional guidelines for prophylaxis and symptom management of TLS.

Participants should be assessed for TLS risk prior to each dose, including evaluation of tumor burden, comorbidities, and renal function, and prior to each dosing with GSK3745417 should be admitted to hospital the day before first dose of each induction cycle or maintenance dose, and receive prophylaxis for TLS in line with institutional guidance. Blood clinical chemistry must be monitored every 6 hours for the first 48 hours of the first dosing cycle, and each cycle with a dose increase. Participants are hospitalized throughout the 2-week dosing period of each induction treatment cycle and TLS prophylaxis should continue alongside daily dosing of GSK3745417 as clinically indicated.

Assessment	Result Range
Uric acid	≥476 µmol/L (≥8.0 mg/dL) or 25% increase from baseline
Potassium	≥6.0 mmol/L or 25% increase from baseline
Phosphorus	≥1.45 mmol/L (≥4.5 mg/dL; adults) or 25% increase from baseline
Calcium	≤1.75 mmol/L (≤7.0 mg/dL) or 25% decrease from baseline

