#### Cairo-Bishop clinical tumor lysis syndrome definition\* and grading

ULN: upper limit of normal; HF: heart failure; ADL: activities of daily living.

\* Clinical tumor lysis syndrome defined as laboratory tumor lysis syndrome plus at least one clinical complication.

¶ Not directly or probably attributable to therapeutic agent.

 $\Delta$  If no institutional ULN is specified, age/sex ULN creatinine may be defined as follows: >1 to <12 years of age, both male and female, 61.6 mmol/L; >12 to <16 years, both male and female, 88 mmol/L; >16 years, female 105.6 mmol/L, male 114.4 mmol/L.

Reproduced with permission from: Coiffier B, Altman A, Pui CH, et al. Guidelines for the management of pediatric and adult tumor lysis syndrome: an evidence-based review. J Clin Oncol 2008; 26:2767. Copyright © 2008 American Society of Clinical Oncology. All rights reserved.

ADR	Adverse drug reaction		
AE	Adverse event		
ALT	Alanine aminotransferase		
AML	Acute myeloid leukemia		
AST	Aspartate aminotransferase		
CNS	Central nervous system		
CRP	C-reactive protein		
CRS	Cytokine Release Syndrome		
CV	Cardiovascular		
СҮР	Cytochrome P450		
DMPK	Drug Metabolism and Pharmacokinetics		
DNA	Deoxyribonucleic acid		
ECG	Electrocardiogram		
EU	European Union		
FTIH	First Time in Humans		
GSK	GlaxoSmithKline		
HPLC/MS/MS	High performance liquid chromatography with tandem mass		
	spectrometry		
IB	Investigator's Brochure		
ICH	International Conference on Harmonization		
IFN	Interferon		
IL	Interleukin		
IV	Intravenous		
MABEL	Minimum anticipated biological effect level		
MC	Multicenter		
ND	Not determined		
OATP	Organic anion transporter polypeptide		
OL	Open label		
PD	Pharmacodynamic		
PD-1	Programmed death receptor 1		
PEG	Polyethylene glycol		
P-gp	P-glycoprotein		
РК	Pharmacokinetic		
RP2D	Recommended Phase 2 Dose		
SAE	Serious adverse event		
SD	Standard deviation		
SOC	System organ class		
STING	STimulator of InterferoN Genes		
TBK1	TANK binding kinase-1		
TK	Toxicokinetic		
TNF	Tumor necrosis factor		
Treg	T-regulatory		
WBC	White blood cell		

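### For renal injury from tumor lysis syndrome (TLS), Section 6.4.1 holds daily dosing at Grade 3, while Table 13 allows dosing to continue if the Medical Monitor agrees, with no grade limit; neither is said to govern, and the section cited for holds contains no hold rule.

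*Protocol*

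**What the plan says.** Protocol Section 6.4.1, under the heading on holding daily dosing, opens with "Daily dosing will be continued unless there is evidence of ongoing TLS or immune activation in line with the criteria below". The first criterion is "Ongoing Grade 3 TLS (see Appendix 11 for Cairo Bishop grading) or Grade 3 electrolyte abnormalities that are not responding to treatment". It mentions no exception for TLS-related creatinine and no Medical Monitor override. The last item in the list lets the investigator hold on clinical judgement.

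Table 13 in Section 7.1.2 has a row triggered by "Serum Creatinine Increase by >0.3 mg/dL or 26.5 µmol/L Compared to Baseline". Its first instruction is "Hold Study Treatment unless considered related to TLS (see Section 6.4.1.2". Further down the row, for renal injury judged secondary to TLS, "treatment may be continued (without hold) with the agreement of the Medical Monitor". The row sets no upper grade and does not refer to the Section 6.4.1 list.

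Section 4.1, and the synopsis in the same words, says that "guidance in Section 6.4.1.2 must be followed to determine when daily dosing should be held". Section 6.4.1.2 covers diagnosis, risk assessment before dosing, prophylaxis, chemistry monitoring and the laboratory and clinical definitions. On conduct once TLS occurs it says "Investigators should use clinical judgement and follow institutional guidelines for prophylaxis and symptom management of TLS". It states no criterion for holding a dose. The TLS row of Table 5 does point to the parent Section 6.4.1 for holding.

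**The concern.** TLS is one of the named risks in Table 5, and holding doses is one of the listed mitigations. Suppose a participant in an induction cycle has laboratory TLS and a creatinine of 4 x ULN. A site reading Section 6.4.1 holds. A site reading Table 13 may ask the Medical Monitor to agree to continue. Participants with the same findings could therefore be managed differently according to the page consulted.

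The route to the right page is also unreliable. The dosing row of the Schedule of Activities sends the site to Section 4.1 for the parameters to review before each daily dose. Section 4.1 sends it on to Section 6.4.1.2, where the trail ends without a hold rule.

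The main stake is participant safety. The secondary stake is interpretation of Part 1. The SAP (Section 4.5.1) derives the number of induction cycles as doses received divided by 10, so each held dose lowers that figure by 1/10 = 0.1 cycle. The documents also leave open whether continuing in Grade 3 TLS with Medical Monitor agreement departs from Section 6.4.1.

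**Working it through.** The plan gives no figure to reproduce. The check is whether both rules reach the same participant and whether any text ranks them.

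**1. Rules by grade, creatinine limb of Appendix 11**

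| TLS grade | Section 6.4.1 hold list | Table 13, rise judged TLS-related |
|---|---|---|
| 1 (1.5 x ULN) and 2 (>1.5 to 3.0 x ULN) | No hold on TLS grade | Exempt from renal hold; may continue if the Medical Monitor agrees |
| 3 (>3.0 to 6.0 x ULN) | Hold if ongoing, subject to step 3 | Same allowance |
| 4 (>6.0 x ULN) | Not named; investigator judgement | Same allowance |

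The rules differ at Grade 3. At Grade 4 the list is silent on TLS grade. At Grades 1 and 2 there is no conflict on TLS grade.

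**2. Does every Grade 3 value also meet the Table 13 trigger?** Inputs are the default ULNs in the Appendix 11 footnote, "female 105.6 mmol/L, male 114.4 mmol/L", and the 26.5 µmol/L trigger. The footnote prints mmol/L; I read the values as µmol/L, which is an assumption.

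- Lower edge of Grade 3 = 3.0 x ULN: 3.0 x 105.6 = 316.8 (female); 3.0 x 114.4 = 343.2 (male).
- Rise from a baseline at the ULN: 316.8 - 105.6 = 211.2; 343.2 - 114.4 = 228.8.
- Ratio to the trigger: 211.2 / 26.5 = 8.0; 228.8 / 26.5 = 8.6.
- Baseline above which a value at the edge of Grade 3 could miss the trigger: 316.8 - 26.5 = 290.3, or 290.3 / 105.6 = 2.7 x ULN (female); 343.2 - 26.5 = 316.7, or 316.7 / 114.4 = 2.8 x ULN (male).

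From any baseline at or below the ULN, a Grade 3 creatinine always falls in the Table 13 row as well. Appendix 11 requires laboratory TLS plus a clinical complication, so the overlap assumes laboratory TLS is present. Table 13's own example, creatinine rising together with phosphate and uric acid, describes that kind of case.

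**3. The qualifier.** In the Section 6.4.1 criterion, the closing phrase about not responding to treatment may modify only the electrolyte abnormalities, or the TLS as well.

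- Electrolytes only: the conflict covers all ongoing Grade 3 TLS with renal injury.
- Both: it covers only Grade 3 TLS that is not responding. It does not vanish, because Table 13 carries no condition on response.

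**4. Is there a ranking?** Section 6.4.1 does not mention Table 13. Table 13 does not mention the hold list, and the section it cites has no hold criterion. No passage says which prevails.

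**5. Is the case foreseen?** Yes. Table 7 exempts from the DLT definition Grade 3 renal injury from TLS that improves with management. It does not say whether doses are held meanwhile.

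**The case against.** The best defence is a layered reading. Table 13 starts at a small creatinine rise, lifts only the renal hold when TLS is the cause, and leaves TLS to its own guidance. It never orders a dose: continuing is optional and needs the Medical Monitor's agreement, so a site that holds complies with both passages and no site can use the allowance alone. This has force. It rules out describing the passages as opposite commands, and central agreement should reduce differences between sites. It does not settle the matter, because the layering is unstated, the cross-reference cannot confirm it, and a site following Section 6.4.1 holds without asking anyone.

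It is also fair that the pointer error is editorial, that Table 5 cites the right section, and that Table 5 lists other TLS mitigations, such as admission for prophylaxis, in-hospital monitoring and eligibility limits.

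Four stronger readings are tempting, and the documents do not support them:

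- *Held doses could make a participant non-evaluable for DLT under the 70% rule.* Section 4.1.1 and SAP Section 3 apply that rule only to doses missed for reasons other than toxicity.
- *Held doses could cost a participant the 7-of-10 gate for intra-patient escalation.* Sections 4.1.2 and 6.4.1.1 already bar escalation after Grade 3 or higher TLS, whatever the dose count.
- *Three of ten doses are in dispute because the DLT rule allows 72 hours.* That period decides whether TLS counts as a DLT. It is not a dosing window, and Days 6 and 7 are undosed anyway.
- *Grade 4 TLS has no route to a hold.* The investigator-judgement item remains, and Section 6.4.1.2 requires TLS risk, including renal function, to be assessed before each dose. What is missing is a named criterion.

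**Conclusion.** The concern stands in a limited form. For ongoing Grade 3 TLS with renal injury, the protocol contains both a hold rule without a stated override and an uncapped allowance to continue with Medical Monitor agreement, and it does not rank them. Depending on the qualifier, the overlap is all ongoing Grade 3 TLS with renal injury or only the non-responding part. Grade 4 is not named in the hold list. Three places (synopsis, Section 4.1, Table 13) cite a section without a hold criterion.

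The overlap calculation assumes the default ULNs are in µmol/L, a baseline at or below the ULN, and laboratory TLS. The documents do not show that any participant was affected. SAP Section 4.8 records that the study was terminated just as Part 1 finished recruiting, so the remaining practical effect is mainly on how Part 1 dose holds and exposure are read.

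**What to change.** In the protocol:

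- Reconcile the Section 6.4.1 hold list with the TLS allowance in Table 13, and state whether that allowance is subject to the Section 6.4.1 criteria.
- State what applies at Grade 4 TLS.
- Make clear whether the phrase about not responding to treatment qualifies TLS, electrolyte abnormalities or both.
- Correct the references to Section 6.4.1.2 in the synopsis, Section 4.1 and Table 13 so that they lead to the section containing the hold rule.

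Which clinical rule should apply is for the sponsor's clinical team.

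The cost is wording in the synopsis and Sections 4.1, 6.4.1 and 7.1.2, with no new procedures, data or sample size. As the study has been terminated, the clinical study report could also state, for any TLS-related renal event in Part 1, whether dosing was held or continued and under which passage.

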## 7.1.3. QTc Stopping Criteria

The QTcF correction formula will be used for *each individual participant* to determine eligibility for and discontinuation from the study. This formula may not be changed or substituted once the participant has been enrolled. If an ECG demonstrates a prolonged QTcF interval, then obtain 2 more ECGs over a brief period and then use the averaged QTcF values of the 3 ECGs to determine whether the participant should be discontinued from the study.

If a participant meets either of the following criteria, they must be discontinued from study treatment.

• QTcF > 500 msec

OR

• Change from baseline of QTcF >60 msec

For participants with underlying **bundle branch block**, proceed with the following discontinuation criteria:

Baseline QTcF with Bundle Branch Block	Discontinuation QTcF with Bundle Branch Block
<450 msec	≥500 msec
450 – 480 msec	≥530 msec

QTcF = QT duration corrected for heart rate by Fridericia's formula

If a clinically significant finding is identified (including, but not limited to changes from baseline in QT interval corrected using [Bazett's formula [QTcB] or Fridericia's formula [QTcF]]) after enrollment, the investigator or qualified designee will determine if the participant can continue in the study and if any change in participant management is needed. This review of the ECG printed at the time of collection must be documented. Any new clinically relevant finding should be reported as an AE.

## 7.1.4. Temporary Discontinuation

Please refer to Section 7.1.5 for information on rechallenge following a liver stopping event.

## 7.1.5. Rechallenge

## 7.1.5.1. Study Intervention Restart After Liver Stopping Criteria Met

Study intervention restart after liver chemistry stopping criteria are met is allowed in this study. Study intervention rechallenge after liver chemistry stopping criteria are met by any participant in this study is not allowed.

If participant meets liver chemistry stopping criteria, do not restart participant with study intervention unless:

- GSK Medical Governance approval is granted
- Ethics and/or IRB approval is obtained, if required, and
- Separate consent for intervention restart is signed by the participant and participant is informed of any associated risks Refer to Appendix 7 for details on restart process.
- If GSK Medical Governance approval to restart participant with study intervention is **not granted**, then participant must permanently discontinue study intervention and should continue in the study for protocol-specified follow up assessments.

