	Grade 3 or 4	Permanently discontinue 	
 
Administer corticosteroids (initial dose of 1-2 mg/kg methylprednisolone or equivalent) followed by taper
 
	See Section 10.7 for additional details on Liver Event Follow-Up Assessments
Type 1 diabetes mellitus (T1DM) or Hyperglycemia	Grade 3-4 hyperglycemia or T1DM (associated with	Restart dosing in appropriately managed, clinically and metabolically stable patients; insulin replacement therapy is required.	
 
Initiate insulin replacement therapy for participants with T1DM
 
Administer antihyperglycemic in participants with hyperglycemia
 
	
 
Monitor participants for hyperglycemia or other signs and symptoms of diabetes.
 

General instructions: 1. Corticostero 2. For severe a by corticoste	bid taper may be initia and life-threatening ir eroids.	ated upon AE improving to Grade 1 or less as per invertex. AEs, IV corticosteroid should be initiated first follower	estigator judgement and institutional treatment gu d by oral steroid. Other immunosuppressive treat	uidelines tment should be initiated if irAEs cannot be controlled
Immune-related Aes	Toxicity grade or conditions	Action taken±	irAE management with corticosteroid and/or other therapies	Monitor and follow-up
	metabolic acidosis or ketonuria)β			
Hypophysitis	Grade 2 or 3	For Grade 2-3, hold until administration of hormonal therapy results in return to adequate hormone levels based on laboratory values and restart dosing when toxicity resolves to Grade 0-1. For recurrence or worsening of ≥ Grade 2 hypophysitis after steroid taper has been completed and patient is on adequate hormone replacement therapy, permanently discontinue.	
 
Administer corticosteroids and initiate hormonal replacements as clinically indicated.
 
	
 
Monitor for signs and symptoms of hypophysitis (including hypopituitarism and adrenal insufficiency)
 

	Grade 4	Permanently discontinue		
Hyperthyroidism	Grade 3	Hold until administration of hormonal therapy results in return to adequate hormone levels based on laboratory values and restart dosing when toxicity resolves to Grade 0-1.	Treat with non-selective beta-blockers (e.g., propranolol) or thionamides as appropriate	
 
Monitor for signs and symptoms of thyroid disorders.
 

	Grade 4	Permanently discontinue 		

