	Grade 3 or 4	Permanently discontinue	
 
Start treatment with prednisone; if persistent G2 beyond 1 week, prednisone/methylprednisone
 
Consider adding one of the following after 1 week of steroids: azathioprine, cyclosporine, cyclophosphamide, infliximab, mycophenolate
 
	
 
Ensure adequate evaluation (eg., nephrology consultation, renal biopsy) to confirm etiology and/or exclude other causes.
 
Consider inpatient care
 

Recurrence of Aes	Grade 1 or 2	Withhold	Based on severity of Aes, administer	
≤Grade 1	Grade 3 or 4	Permanently discontinue	appropriate treatment until symptoms improve to ≤Grade 2	
NOTES	•	•		

The decision whether to withhold or permanently discontinue GSK3745417 is at the discretion of the investigator or treating physician.
 For participants with Grade 3 or 4 immune-related endocrinopathy where interruption of GSK3745417 is required, treatment with GSK3745417 may be resumed when the event resolves to Grade ≤2 and is controlled with hormonal replacement therapy or, for T1DM, metabolic control has been achieved.

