## 10.7.1. Study Treatment Restart or Rechallenge

If participant meets liver chemistry stopping criteria do not restart participant with study treatment unless:

- GSK Medical Governance approval is granted (as described below),
- Ethics and/or IRB approval is obtained, if required, and
- Separate consent for treatment restart/rechallenge is signed by the participant

If GSK Medical Governance approval to restart participant with study treatment **is not granted**, then participant must permanently discontinue study treatment and may continue in the study for protocol-specified follow up assessments for overall survival.

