# 10.7.2. Restart Following Transient Resolving Liver Stopping Events Not Related to Study Treatment

Restart refers to resuming study treatment following liver stopping events in which there is a clear underlying cause (other than DILI) of the liver event (e.g., biliary obstruction, pancreatic events, hypotension, acute viral hepatitis). Furthermore, restart is not permitted following liver stopping event when the underlying cause was alcoholic hepatitis.

Approval by GSK for study treatment restart can be considered where:

- Investigator requests consideration for study treatment restart if liver chemistries have a clear underlying cause (e.g., biliary obstruction, hypotension and liver chemistries have improved to normal or are within 1.5 × baseline and ALT <3×ULN).
- Possible study treatment-induced liver injury has been excluded by the investigator and the study team. This includes the absence of markers of hypersensitivity (otherwise unexplained fever, rash, eosinophilia). Where a study treatment has an identified genetic marker associated with liver injury (e.g., lapatinib, abacavir, amoxicillin/clavulanate), the presence of the marker should be excluded. If study treatment-related liver injury cannot be excluded, the guidance on rechallenge in Section 10.7.2 will apply.
- There is no evidence of alcoholic hepatitis.
- Ethics Committee or Institutional Review Board approval of study treatment restart must be obtained, as required.
- If restart of study treatment is approved by GSK Medical Governance in writing, the participant must be provided with a clear description of the possible benefits and risks of study treatment administration, including the possibility of recurrent, more severe liver injury or death.
- The participant must also provide signed informed consent specifically for the study treatment restart. Documentation of informed consent must be recorded in the study chart.
- Study treatment must be administered at the dose specified by GSK.
- Participants approved by GSK Medical Governance for restarting study treatment must return to the clinic once a week for liver chemistry tests until stable liver chemistries have been demonstrated and then laboratory monitoring may resume as per protocol.
- If after study treatment re-start, participant meets protocol-defined liver chemistry stopping criteria, follow usual stopping criteria instructions.

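### Table 12 gives two conflicting restart rules for Grade 3-4 immune-related endocrinopathy; the liver rechallenge text needs a lesser, cross-reference correction

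*Protocol*

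**What the plan says.** **Endocrine events (Protocol Section 6.4.1.7, Table 12).** The rows for hypophysitis (Grade 2-3), hyperthyroidism (Grade 3), hypothyroidism (Grade 3) and adrenal insufficiency (Grade 2-3) hold dosing until hormone levels are adequate and then "restart dosing when toxicity resolves to Grade 0-1". At Grade 4 all four rows call for permanent discontinuation. A note under the table addresses Grade 3 or 4 endocrinopathy in which dosing has to be interrupted, and says "treatment with GSK3745417 may be resumed when the event resolves to Grade ≤2 and is controlled with hormonal replacement therapy", with a separate condition of metabolic control for type 1 diabetes. Another note leaves the choice between withholding and permanent discontinuation to the investigator or treating physician.

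**Liver events (Protocol Section 7.1.5.1 and Appendix 7).** Section 7.1.5.1 draws a distinction: "Study intervention restart after liver chemistry stopping criteria are met is allowed in this study", whereas "Study intervention rechallenge after liver chemistry stopping criteria are met by any participant in this study is not allowed". The action table in Section 10.7 makes restart or rechallenge depend both on the protocol allowing it and on approval by the sponsor's medical governance; failing either, treatment stops permanently. Section 10.7.1 lists among its conditions "Separate consent for treatment restart/rechallenge is signed by the participant". Section 10.7.2 confines restart to events with a clear cause other than drug-induced injury, requires that "Possible study treatment-induced liver injury has been excluded by the investigator and the study team", and adds "If study treatment-related liver injury cannot be excluded, the guidance on rechallenge in Section 10.7.2 will apply".

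**The concern.** A table of this kind is used at the bedside to decide whether a participant is dosed again. If the row and the note under it give different thresholds, two sites can follow the protocol and handle the same course of events differently. Immune-related events are a named risk of the drug in Protocol Table 5, so the decision bears on safety.

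It also reaches the reported results. Withdrawals due to adverse events are part of the Part 1 primary endpoint in both the Protocol and the SAP, and SAP Section 6.1.1 tabulates discontinuation of study intervention with its primary reasons. A discontinuation that depends on which line of Table 12 was applied cannot be interpreted without knowing which line that was.

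The liver text raises a related question. The main body forbids rechallenge, yet the appendix speaks of rechallenge consent and rechallenge guidance for the very case in which drug causation is still possible.

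**Working it through.** No arithmetic applies. The check is to set the passages side by side.

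**1. Endocrine rows against the note**

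| Situation | Table 12 row | Note under Table 12 |
|---|---|---|
| Grade 3 hypophysitis, hyperthyroidism, hypothyroidism or adrenal insufficiency, now Grade 2 and controlled on hormone replacement | Keep holding until Grade 0-1 | May resume, since Grade 2 meets the Grade 2-or-lower condition |
| Grade 4 event in any of the same four | Permanently discontinue | Names Grade 4; may resume at Grade 2 or lower if controlled |
| Grade 3-4 hyperglycemia or type 1 diabetes | Restart when clinically and metabolically stable, with insulin | Metabolic control achieved |

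The first line is a direct conflict. The second is a conflict if the note applies to those rows. The third line agrees.

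**2. Is the note only about diabetes?** No. It gives type 1 diabetes its own condition. The clause on Grade 2 or lower with hormone replacement must therefore govern other endocrinopathies.

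**3. A by-product of the conflict.** The note covers index events of Grade 3 or 4 only. A Grade 2 hypophysitis or adrenal insufficiency stays under its row and must reach Grade 0-1. A Grade 3 event may, under the note, resume while still at Grade 2. Read together, the milder event meets the stricter threshold.

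**4. How far does the note reach at Grade 4?** This cannot be settled from the text. The note is limited to events in which interruption is required, which could be read as excluding events already marked for permanent discontinuation. Yet it names Grade 4 expressly. Footnote markers were damaged when the PDF was read: one survives at the hyperthyroidism Grade 4 entry, none shows at the hypophysitis, hypothyroidism or adrenal Grade 4 entries, and the notes have lost their labels. A deliberate exception for hyperthyroidism is possible.

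**5. Liver sections read in sequence**

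- Restart needs drug-induced injury to be excluded (Section 10.7.2). If it is not excluded, restart is unavailable.
- Rechallenge is barred for every participant (Section 7.1.5.1).
- Where neither is allowed by the protocol, treatment stops permanently (action table, Section 10.7).

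The sequence ends in one answer. Two drafting faults remain. Section 10.7.2 refers to Section 10.7.2 for rechallenge guidance, but that section concerns restart and holds none. Section 10.7.1 is headed and worded as if rechallenge were available, which does not fit Section 7.1.5.1.

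**The case against.** The best defence of Table 12 is that the note is a specific qualification of general rows: it applies to a narrow group, controlled on replacement therapy, and another note openly gives the investigator discretion. Damaged footnote markers also mean that some apparent conflict may come from the text extraction. Part of this stands. The Grade 4 reading has to be stated with reserve, and some variation between investigators is intended. It does not remove the Grade 3 conflict. Four rows set Grade 0-1, the note sets Grade 2 or lower, and nothing in the text says that the note overrides those rows. Discretion over withholding or stopping does not tell the reader which resolution grade permits restart.

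Three stronger readings are tempting and are not supported.

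- *A reader might infer that participants with liver events get opposite answers, or are re-dosed at one site and stopped at another.* The sections together give one answer, the circular pointer opens no route to re-dosing, and restart requires sponsor medical governance approval, separate consent and, where required, ethics approval. No site decides alone.
- *A reader might infer that every participant with Grade 3-4 endocrinopathy settling at Grade 2 is affected.* The diabetes and hyperglycemia row agrees with the note.
- *A reader might infer that the conflict distorts the RP2D.* The documents do not show this. The MTD rests on DLTs within 28 days (Section 4.1), and the immune-related DLT criterion in Table 7 has its own clock, resolution to Grade 1 or baseline within 8 days, whatever is decided later about restart.

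**Conclusion.** The endocrine conflict is real and should be corrected. It covers four rows of Table 12: certain for a Grade 3 event that has settled at Grade 2 on hormone replacement, and possible, depending on the note's scope, for Grade 4. The liver point is a secondary correction: a circular cross-reference and rechallenge wording that does not match Section 7.1.5.1, within a set of rules that otherwise reaches a single result.

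The numerical effect cannot be given, because the documents report no frequency of such events in this study. A cohort may hold as few as three participants (Section 4.1), so one participant handled differently would move that cohort's discontinuation proportion by 1/3. That illustrates sensitivity and is not an estimate of bias.

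Practical weight is limited by timing. SAP Section 4.8 records that the study was terminated just as Part 1 finished recruitment and that Part 2 will not recruit. The conclusion assumes that the lost footnote labels do not contain an explicit statement of which rows the note overrides; if the original PDF shows one, the Grade 4 part should be reread.

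**What to change.** 1. Reconcile the Table 12 rows for hypophysitis, hyperthyroidism, hypothyroidism and adrenal insufficiency with the note under the table, so that one resolution grade and one Grade 4 action apply, and state which rows the note covers. This review does not say which rule should stand.
2. Reconcile Sections 10.7.1 and 10.7.2 with Section 7.1.5.1, so that one statement on liver rechallenge appears throughout, and correct the reference in Section 10.7.2 that leads back to itself.
3. In the study report, state which restart rule was applied to any participant with an affected endocrine event, or that there was none.

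The cost is protocol wording, a short clarification to sites with participants still on treatment, and a sentence in the report. No sample size, analysis or data collection changes. The corrected text should also be used if the table or the appendix is carried into another protocol.
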